7.7 EXTENT OF EXPOSURE

Extent of exposure will be explored based on total treatment time, calculated from start to end of treatment, including off-drug periods due to non-compliance or toxicity prior to permanent discontinuation. For methotrexate, time between the weekly infusions will be counted toward total treatment time. Standard descriptive summaries, by treatment group, of these data will be provided for all treated patients (the treated set), according to the initial treatment taken.

Kaplan-Meier curves will be calculated to show the time from treatment start to permanent discontinuation, the number of patients at risk (exposed) during the study treatment period.

Dose escalation and reductions are allowed in all patients, details in Section 4 of the CTP. Exposure will also be summarised by dosing level:

- Treatment time by each dose level (50, 40, 30 and 20). Dose level unit is mg for afatinib and mg/m² for methotrexate.
- Number and proportion of patients on each dose level over time.
- Time to first dose reduction, Kaplan-Meier plot of time from first dose of study medication to the first dose reduction
- For afatinib, duration of off-drug periods prior to dose reduction.

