All patients will visit the investigational site weekly for assessment of safety parameters and AEs. Tumour response will be assessed regularly by CT scan/MRI (see [Flow Chart](#)) until progression. At disease progression, confirmed by tumour imaging, patients will be discontinued from the study medication.

The end of treatment (EOT) is defined as permanent discontinuation of Afatinib or methotrexate. Related EOT information needs to be obtained. Patients who permanently discontinue the study medication for any other reason than progression of disease (or withdrawal of consent) should continue the scheduled tumour imaging visits until progression as described in [Section 6.2.3](#). The requirement to continue imaging for study purposes for such patients will be removed following the database lock for primary analysis.

Following the EOT visit, patients should come to a follow-up visit (FUV) and then continue in the observational period. During the observational period, data of survival (vital status), related SAEs/AESIs and concomitant anti-cancer therapy will be collected. For patients who progressed on treatment, the observation period for overall survival starts after the FUV (end of residual effect) visit. For patients who have not progressed on treatment, this period starts after the last additional FU visit. A patient is considered to have completed the trial following death, withdrawal of consent or lost to follow-up.

Primary statistical analyses will be performed when the required number of progression free survival events has occurred as described in [Section 7.6](#). The clinical trial report will be written based on primary analysis results. An addendum to the clinical trial report may be used to summarise data collected beyond database lock for the primary analysis.

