3.3.4 Removal of patients from this trial or assessments

3.3.4.1 Removal of individual patients

A patient is to be permanently discontinued from study medication if:

1. The patient withdraws consent to further study medication.
2. Radiologically documented progressive disease (refer to [Section 5.1.2](#)).
3. Pregnancy (refer to [Section 5.2.2.2.1](#)).
4. Diagnosis of ILD.
5. Need further dose reductions but not allowed according to the protocol (see [Section 4.1.4](#)).

Proprietary confidential information. © 2019 Boehringer Ingelheim International GmbH or one or more of its affiliated companies

6. The patient is no longer able to receive the study medication (e.g. adverse events, concomitant diagnoses, concomitant therapies interfering with Afatinib or methotrexate, or administrative reasons), significant deviation from the protocol.

At the time of study medication withdrawal the patient should return for a complete EOT visit. The information, including the reason for treatment discontinuation, will be recorded in the electronic Case Report Form (eCRF). See also [Section 6.2.3](#) and the [Flow Chart](#).

For safety reasons, the patient should come to the FUV four weeks after the EOT visit. Following the FUV, the patient will continue in the observational period. During this period vital status information, anti-cancer therapy, and related SAEs and AESIs will be collected every four weeks. For patients who progressed on treatment, the observation period for overall survival starts after the FUV (end of residual effect) visit. For patients who have not progressed on treatment, this period starts after the last additional FU visit. The observational period ends when the patient deceases.

A patient should be withdrawn from trial if:

1. The patient withdraws consent for any further trial procedures and follow-up activities.

Data of a withdrawn patients, regardless the patient received study medication or not, and the reason of withdrawal must be recorded in the eCRF.

Unless a randomised patient withdraws consent to be followed up, vital status information will be collected (e.g. by phone contact or check of medical records) until the entire trial has ended.

Patients who withdraw from the trial after randomization will not be replaced.

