The dose of Afatinib must be escalated to 50 mg (at the earliest after 28 days on study medication) if all the following criteria are met:

- CTCAE grade ≤ 1 skin rash (any aetiology/relation)
- Absence of diarrhoea, mucositis, and/or any drug-related event (any grade) other than skin rash CTCAE grade 1 and
- Compliance of Afatinib intake is in 80~100% as described in [Section 4.3](#)
- Dose was not previously reduced due to any of the AEs depicted in the dose reduction scheme (see [Table 4.1.4.1: 1](#))

Dose escalation is prohibited in any situation other than that described above. The patient should remain on 50 mg unless dose reduction becomes necessary (see Table 4.1.4.1: 1).

Dose reduction, Afatinib

Treatment related AEs will be managed by treatment interruptions and subsequent dose reductions of Afatinib according to the schedule described in Table 4.1.4.1: 1. Dose reductions

Proprietary confidential information. © 2019 Boehringer Ingelheim International GmbH or one or more of its affiliated companies

will apply to individual patients only. Once the dose has been reduced, it may not be increased later.

Table 4.1.4.1: 1 Afatinib dose reduction scheme

| AE type and CTCAE grade |
|--|
| Events related to study medication; 
• Any drug related AE grade ≥ 3.• Diarrhoea grade ≥ 2 persisting for 2 or more consecutive days (≥ 48 hours) despite adequate anti-diarrhoeal medication/hydration.• Nausea and/or vomiting grade ≥ 2 persisting for 3 or more consecutive days despite anti-emetic treatment/hydration.• Reduced renal function to grade ≥ 1 as measured by serum creatinine, proteinuria, or glomerular filtration rate. |
| Action |
| Interrupt Afatinib treatment until patient has recovered to grade ≤ 1 (note for reduced renal function, recovered to grade <1) or to the CTCAE grade present at baseline ¹ . If patient has not recovered within 14 days, study medication should be permanently discontinued ² . |
| Dose reduction scheme |
| Resume treatment at reduced dose according to; 
• 40 mg if the dose prior to the interruption was 50 mg.• 30 mg if the dose prior to the interruption was 40 mg.• 20 mg if the dose prior to the interruption was 30 mg. No dose reduction is allowed below 20 mg. |

1 Baseline is defined as the CTCAE grade prior to start of treatment

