6.6 HANDLING OF MISSING DATA AND OUTLIERS

In general, missing efficacy data will not be imputed and all reasonable efforts will be taken during the study conduct to obtain such data. Patients lost to follow up, with unknown vital status, missing tumour imaging data etc. will be censored for time to event analyses. Detailed rules for censoring are provided in [Table 7.4: 1](#).

Missing or incomplete AE dates are imputed according to BI standards (see “Handling of missing and incomplete AE dates”)[[2](#)].

Handling of missing PK data will be performed according to BI standards (see “Standards and processes for analyses performed within Clinical Pharmacokinetics/Pharmacodynamics”)[[11](#)].

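### The Kaplan-Meier plot of time to first dose reduction (SAP 7.7) has no rule for patients who stop drug or die unreduced; if they are censored at last dose, it overstates the share reduced

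*SAP*

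**What the plan says.** SAP 7.7 plans the following display for the treated set: "Time to first dose reduction, Kaplan-Meier plot of time from first dose of study medication to the first dose reduction". It gives no censoring rule and no competing-event method.

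The general rule in SAP 6.6 does not fill the gap: "Patients lost to follow up, with unknown vital status, missing tumour imaging data etc. will be censored for time to event analyses". It then refers to the PFS table for details. Stopping drug is not mentioned. By contrast, the SAP does state the handling for PFS (Table 7.4: 1), for overall survival and for HRQoL time to deterioration (both 7.5.2).

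The protocol makes stopping final. Section 3.1 says: "The end of treatment (EOT) is defined as permanent discontinuation of Afatinib or methotrexate". Section 3.3.4.1 lists the reasons, which include progression as well as toxicity. For afatinib, the reduction scheme in 4.1.4.1 holds treatment until recovery and then resumes at a lower dose, but it also says: "If patient has not recovered within 14 days, study medication should be permanently discontinued". A footnote allows an exception by agreement between sponsor and investigator. For methotrexate, 4.1.4.2 ends treatment when a drug-related event needs a pause of more than three consecutive weeks.

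SAP 7.7 also plans total treatment time by group, Kaplan-Meier curves of time to permanent discontinuation with numbers exposed, treatment time at each dose level, and "Number and proportion of patients on each dose level over time". SAP 7.8.1 adds a frequency table, by treatment, of patients with adverse events that led to a dose reduction.

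**The concern.** A patient who has stopped drug for good cannot have a first dose reduction afterwards. Kaplan-Meier with censoring at last dose treats that patient as someone who could still be reduced later, at the same rate as patients who remain on drug. The height of the curve is then not a proportion of patients.

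Stopping is also informative. The toxicity that would lead to a reduction can lead to a stop instead, in either arm. The height of a censored curve could be read as the probability of reduction if nobody stopped, but only if stopping were unrelated to the prospect of a reduction. The dose rules suggest that it is related.

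At stake is a tolerability message. A reader will tend to take the curve as the percentage of patients who needed a lower dose after starting at 40 mg or 40 mg/m². No endpoint or test depends on it.

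**Working it through.** **Stated figures.** The documents give no dose-reduction rate and no treatment duration for this trial, so there is no plan figure on this point to reproduce. The only usable inputs are the planning PFS medians in Protocol 7.6: 3.0 months (afatinib) and 2.1 months (methotrexate), exponential, with hazard ratio 2.1/3.0 = 0.70. As a check on how those inputs are read, the Schoenfeld formula with one-sided alpha 0.025, 80% power and 2:1 allocation gives (1.960 + 0.842)² / [(2/3)(1/3)(ln 0.70)²] ≈ 278 events, against 274 stated. That is within 1.5%. The present point does not depend on it.

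**Assumptions that are not in the documents.** Time on drug without a reduction is exponential with the planning PFS medians. The reduction hazard h is constant and equal in both arms, with a range of 0.1 to 0.3 per month. Reduction and stopping are independent.

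**Stopping hazards.** d = ln 2 / median:
- afatinib: 0.693/3.0 = 0.231 per month
- methotrexate: 0.693/2.1 = 0.330 per month

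**Formulas.**
- Censoring at stop: 1-KM = 1 − exp(−h·t)
- Share actually reduced (cumulative incidence, CIF): h/(h+d) × [1 − exp(−(h+d)·t)]

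For h = 0.2 and t = 6 months:
- 1-KM = 1 − exp(−1.2) = 69.9%
- CIF, afatinib = 0.2/0.431 × [1 − exp(−2.586)] = 42.9%
- CIF, methotrexate = 0.2/0.530 × [1 − exp(−3.180)] = 36.2%

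**Results at 6 months.**

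| h per month | 1-KM, both arms | CIF afatinib | Excess, points | CIF methotrexate | Excess, points |
|---|---|---|---|---|---|
| 0.1 | 45.1% | 26.1% | 19 | 21.5% | 24 |
| 0.2 | 69.9% | 42.9% | 27 | 36.2% | 34 |
| 0.3 | 83.5% | 54.2% | 29 | 46.5% | 37 |

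**The other possible handling.** At week 24 (24 × 7/30.4375 = 5.52 months) with h = 0.2, censoring at stop gives 67% in both arms, against a CIF of 42% on afatinib and 36% on methotrexate. A simulation of 400,000 patients per arm gives the same values. If stoppers instead stay in the risk set to the common cut-off, the simulated Kaplan-Meier figures are 42% and 36%, which equal the CIF. The whole excess therefore comes from the choice that the SAP leaves open.

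**Unequal hazards.** With h = 0.3 on afatinib the excess is 29 points. With h = 0.1 on methotrexate it is 24 points. The arm with the larger excess changes with the hazards.

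**The case against.** The best defence is that the SAP never says stoppers are censored at last dose, that the display is descriptive, and that the tolerability message is available elsewhere. Much of this stands, and it rules out several stronger readings that a reader might infer.

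- **That the curve will certainly be too high.** The text does not support this. The handling is unstated, and one admissible handling gives no excess. Against that, censoring at last dose is usual, and SAP 7.7 equates being at risk with being exposed for its discontinuation curve.
- **That shorter time on methotrexate is hidden.** The same section shows treatment time and the discontinuation curves with numbers exposed. Shorter treatment on methotrexate is itself only inferred from the planning PFS medians.
- **That nothing else in the SAP gives the share reduced.** SAP 7.8.1 gives the crude share with adverse events leading to reduction. That table has no time axis. It may also miss methotrexate reductions triggered only by the laboratory thresholds in Protocol 4.1.4.2, because 5.2.2.1.6 records laboratory changes as adverse events only when judged clinically relevant. It does give the main tolerability figure.
- **That methotrexate is more affected.** This follows only from the assumed equal hazards. The reduction triggers in 4.1.4.1 and 4.1.4.2 differ, so equal hazards have no support in the documents.
- **That time to first onset of special-interest adverse events has the same flaw.** SAP 7.8.1 names no Kaplan-Meier method there and counts events up to 28 days after last intake. Stopping drug does not preclude onset.

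It can also be said that a curve censored at stop legitimately describes reduction among patients still on drug. Its slope does reflect the rate in those patients. Its height is still not a share of patients, and informative stopping weakens any hypothetical reading of it. The choice is therefore more than a matter of taste.

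**Conclusion.** The point holds as a conditional one. SAP 7.7 leaves open how permanent discontinuation or death without a reduction is handled, and both preclude the event being plotted. Under censoring at last dose, 1-KM overstates the share reduced. Under the stated assumptions the excess at 6 months is about 19 to 37 points over hazards of 0.1 to 0.3 per month, with a central illustration of 70% against 43% (afatinib) and 36% (methotrexate). These sizes depend on assumed hazards and on PFS standing in for time on drug, so they show scale and are not a forecast. If stoppers are kept at risk to a common cut-off, the excess is zero. Which arm would be more affected cannot be settled from the documents.

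The importance is low. The effect is limited to one descriptive plot, companion displays already carry most of the information, and neither the primary analysis nor any endpoint is touched.

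**What to change.** In SAP 7.7, replace the Kaplan-Meier plot of time to first dose reduction with a cumulative incidence (Aalen-Johansen) curve for each arm. The event is first dose reduction, and the competing event is permanent discontinuation or death before any reduction. Patients still on drug and not reduced at the cut-off are censored there. Print the numbers at risk by arm beneath the curve. Make no change to the time-to-onset displays in SAP 7.8.1 on this account.

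The cost is a sentence in the SAP and minor extra programming, with no new data. One small downside is that the new curve can no longer be read as a reduction rate among patients still on drug.

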7.8 SAFETY ANALYSIS

All safety analyses will be performed on the treated set.

7.8.1 Adverse events

Unless otherwise specified, the analyses of adverse events (AEs) will be descriptive in nature. All analyses of AEs will be based on the number of patients with AEs and NOT on the number of AEs.

Furthermore, for analysis of AE attributes such as duration, severity, etc, multiple AE occurrences collected on the CRF will be collapsed into AE episodes provided that all of the following applies:

- The same MedDRA lowest level term was reported for the occurrences
- The occurrences were time-overlapping or time-adjacent (time-adjacent if the second occurrence started on the same day or on the day after the end of the first occurrence)
- Treatment did not change between the onset of the occurrences OR treatment changed between the onset of the occurrences, but no deterioration was observed for the later occurrence

For further details on summarization of AE data, please refer to the guideline 'Handling and summarization of adverse event data for clinical trial reports and integrated summaries' [9].

The analysis of adverse events will be based on treatment-emergent adverse events, i.e. all adverse events with an onset date between first drug intake and 28 days after last drug intake. All adverse events occurring before first drug intake will be assigned to 'screening' and all adverse events occurring after last drug intake + 28 days will be assigned to 'post-study'. For details on the treatment definition, see [Section 6.1](#).

An overall summary of adverse events will be presented. This summary will exclude the rows 'Severe AEs', and 'Other significant AEs' but will include additional rows for 'AEs leading to dose reduction', 'AEs leading to permanent discontinuation of study drug', and 'AEs by highest CTCAE grade'.

The frequency of patients with adverse events will be summarised by treatment, primary system organ class (SOC) and preferred term (PT) of MedDRA (using the version that is current at the time of analysis). All tables will be sorted by SOC according to the standard sort order specified by the European Agency for the Evaluation of Medicinal Products (EMEA); PTs will be sorted by frequency (within SOC). Frequency tables will be created for the following events:

- All AEs
- Drug-related AEs
- AEs leading to dose reduction
- AEs leading to treatment discontinuation
- Drug-related AEs leading to treatment discontinuation
- Serious AEs
- Drug-related serious AEs
- Fatal AEs

These tables will be further categorised by highest CTCAE grade, including all grades, Grade 1-5.

In addition, preferred terms have been grouped to capture similar events, e.g. skin reactions that include rash, acne etc. Six grouped terms (rash/acne, stomatitis, ocular effects, lip effects, nail effects and fatigue) have been formulated for afatinib. These grouped terms are carefully reviewed by the Team Member Drug Safety for afatinib for each MedDRA version and maintained at the substance data base. The above frequency tables will be repeated using these grouped terms and remaining MedDRA PTs (i.e. the original PTs under these grouped terms will not be displayed). The tables will be sorted by descending frequency.

Additional AE tables will be produced for AEs of special interest (diarrhoea, the grouped term of rash/acne, stomatitis, renal insufficiency, hepatic impairment, and hematological events), providing further details on highest CTCAE grade, action taken with study drug and time to first onset of AE etc.

In recent trials, it has been observed that patients treated with an EGFR TKI who develop rash events tend to have better response and progression free survival. In order to explore this effect in this study, afatinib-treated patients will be grouped by the occurrence of CTCAE grade ≥ 2 rash/acne events and provide descriptive statistics for objective response and progression free survival. This analysis is exploratory in nature and not for comparison with methotrexate, therefore will be limited to afatinib patients only.

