2.2 TRIAL OBJECTIVES

The objective of this trial is to investigate the efficacy and safety of Afatinib versus methotrexate in the treatment of patients with R/M HNSCC who have progressed after platinum based therapy given for R/M HNSCC. The main objective of the trial is to investigate the favourable trend of Afatinib to methotrexate in terms of PFS improvement as the second line

Proprietary confidential information. © 2019 Boehringer Ingelheim International GmbH or one or more of its affiliated companies

treatment for this trial patient population. Patients on both treatment arms will be allowed to receive best supportive care in addition to study medication.

The secondary objectives are to compare OS, objective response rate (ORR), health related quality of life (HRQOL), and safety of two treatment arms. For details on endpoints and their assessments, see [Section 5](#).

PFS is chosen as the primary endpoint because additional anti-cancer therapy after disease progression dilutes the potential increase in survival afforded by the treatments under investigation. For example, two recent trials have investigated the efficacy of EGFR targeting drugs in the R/M setting: the IMEX trial ([R10-5936](#)) and the ZALUTE trial ([R11-0801](#)). In these trials, up to 38% of patients received further treatment after progression. Also, this primary endpoint is consistent with global pivotal study 1200.43.

Study 1200.161 is phase III trial with a design similar to the global phase III trial 1200.43 (NCT01345682), but to be conducted in the Asian/Middle East and North African (MENA) region.

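### No time-adjusted measure is named for the general AE tables, although the AE window is likely to be about one third longer on afatinib

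*SAP*

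**What the plan says.** Comparing safety is a stated aim. Protocol 2.2 reads: "The secondary objectives are to compare OS, objective response rate (ORR), health related quality of life (HRQOL), and safety of two treatment arms". Protocol 7.3.3 makes the safety analysis descriptive and exploratory.

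SAP 7.8.1 sets the counting unit: "All analyses of AEs will be based on the number of patients with AEs and NOT on the number of AEs". The analysis covers treatment-emergent events, that is, "all adverse events with an onset date between first drug intake and 28 days after last drug intake". For the main tables, "The frequency of patients with adverse events will be summarised by treatment, primary system organ class (SOC) and preferred term (PT) of MedDRA". Eight such tables are listed, including all, serious and fatal AEs and AEs leading to discontinuation, and each is also split by highest CTCAE grade. Under SAP section 7 the default denominator for percentages is the treatment group.

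Two time-related elements are planned:

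- **Special-interest events (SAP 7.8.1).** "Additional AE tables will be produced for AEs of special interest", namely diarrhoea, rash/acne, stomatitis, renal insufficiency, hepatic impairment and haematological events, "providing further details on highest CTCAE grade, action taken with study drug and time to first onset of AE etc".
- **Exposure (SAP 7.7).** "Standard descriptive summaries, by treatment group, of these data will be provided for all treated patients", and "Kaplan-Meier curves will be calculated to show the time from treatment start to permanent discontinuation". These summaries are not tied to the AE tables.

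The Protocol synopsis has both arms treated until progression on imaging or an AE that requires permanent discontinuation.

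**The concern.** The period in which an AE can be counted ends 28 days after the last dose, and treatment normally ends at progression. If afatinib delays progression, as the trial is powered to show, afatinib patients are observed for AEs for longer. A crude percentage then mixes the risk per month with the number of months at risk. The reader of a serious-AE or preferred-term table cannot separate the two.

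Two misreadings are possible. Equal monthly risks can appear as more toxicity on afatinib. Equal percentages can hide a lower monthly risk on afatinib. Both go in a known direction for events that accrue steadily, so they would tend to recur from row to row.

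**Working it through.** **The plan's own figures.** The documents state no AE rate and no expected exposure, so the only figures to reproduce are those for PFS. Protocol 7.6 assumes medians of 3.0 and 2.1 months: 3.0/2.1 = 1.43, the 43% improvement of the synopsis. Schoenfeld's formula with HR 0.70, one-sided 0.025, 80% power and 2:1 allocation gives 278 events against the stated 274. With 274 events, power is 79.5% against the stated 80%. The design figures reproduce closely.

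**Assumptions for the AE check (not in the documents).** Treatment time is exponential with the design PFS medians. The AE hazard L per month is constant, equal in both arms and independent of stopping treatment.

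**Length of the AE window.** Mean treatment time is median/ln 2, so 3.0/0.693 = 4.33 months on afatinib and 2.1/0.693 = 3.03 on methotrexate. The tail is 28/30.44 = 0.92 months. The windows are 5.25 and 3.95 months, a ratio of 1.33. With the medians observed in trial 1200.43 (Protocol 1.2.3: 2.63 vs 1.74) they are 4.71 and 3.43 months, a ratio of 1.37.

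**Crude percentage under equal hazards.** With m = ln 2/median, the proportion with an event is 1 − exp(−0.92 L) × m/(m + L). Here m = 0.231 (afatinib) and 0.330 (methotrexate). At L = 0.2, exp(−0.184) = 0.832, so:

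- afatinib: 1 − 0.832 × 0.231/0.431 = 55.4%
- methotrexate: 1 − 0.832 × 0.330/0.530 = 48.2%

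| L per month | Methotrexate | Afatinib | Gap (points) | Ratio |
|---|---|---|---|---|
| 0.02 | 7.4% | 9.6% | 2.2 | 1.30 |
| 0.05 | 17.1% | 21.5% | 4.4 | 1.26 |
| 0.10 | 30.0% | 36.3% | 6.3 | 1.21 |
| 0.20 | 48.2% | 55.4% | 7.2 | 1.15 |
| 0.50 | 74.9% | 80.0% | 5.2 | 1.07 |
| 1.00 | 90.1% | 92.5% | 2.4 | 1.03 |

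Gaps were computed before rounding. The largest gap is 7.2 points (8.1 with the 1200.43 medians).

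**Masking.** Equal crude percentages of 17.1% in both arms correspond to a hazard ratio of 0.76 for afatinib. At 60.2% the ratio is 0.79. Equal percentages in that range would hide a hazard 21 to 24% lower.

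**Early-onset events.** If the hazard acts only in the first 14 days, the percentages are identical (12.9% in both arms at L = 0.3), because that period lies inside every patient's window. If it acts only in the first 6 weeks they are 33.4% vs 33.2% at L = 0.3.

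**What a person-time rate does.** Under constant equal hazards it gives a ratio of 1.00. It fails for early events. Suppose 30% of each arm have the event in the first 14 days, at day 7 on average (0.23 months). Time at risk per patient is 0.7 × 5.25 + 0.3 × 0.23 = 3.74 months on afatinib and 0.7 × 3.95 + 0.3 × 0.23 = 2.83 on methotrexate. The rates are 0.30/3.74 = 0.080 and 0.30/2.83 = 0.106, a ratio of 0.76. Identical early toxicity would look about 24% lower on afatinib.

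**The case against.** - **The plan is not limited to crude percentages.** A reader might infer that it is. SAP 7.8.1 plans time to first onset for six groups that include the best-known afatinib toxicities, and SAP 7.7 shows exposure by arm. This stands for those groups. It does not reach the general tables, and the form of the time-to-onset summary is not specified. If it covers only patients who had the event, it does not correct for unequal follow-up.
- **The sentence on the counting unit does not forbid time-based methods.** It sets patients against event counts. A rate of first events per patient-month complies with it. This stands: the gap is one of omission.
- **An exposure difference of about 40% is not stated anywhere.** A reader might infer it from the PFS medians. Design PFS rests on central review, while treatment stops on investigator assessment, AEs or other reasons. Even if treatment time equalled PFS, the window that the SAP uses would be about 33% longer, because the 28-day tail is the same in both arms. Figures that leave out the tail describe an analysis that is not planned.
- **A constant hazard is doubtful for many events.** Protocol 1.2.3 says diarrhoea generally begins within two weeks, and Protocol 5.2.2.1.5 has signs and symptoms of progression recorded as AEs, so these cluster near progression. This limits the range of events affected.
- **The gap is smaller than sampling error.** With 220 and 110 patients, the 95% half-width for a difference in proportions is 1.96 × √(0.3 × 0.7 × (1/220 + 1/110)) = 10.5 points at 30%, and 11.4 at 50%. That is true for a single row, but sampling error has no preferred direction and this bias does.
- **A sponsor guideline may cover it.** SAP 7.8.1 refers to one for further detail on AE summaries (reference 9). It is not among the documents, so this remains open.

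**Conclusion.** The point holds as a modest gap in the SAP. No time-adjusted measure is named for the general AE tables, although a longer AE window on afatinib is a direct consequence of the effect that the trial is designed to detect. Under the assumptions above, the bias is at most about 7 points with the design medians and about 8 with those of trial 1200.43. The ratio is about 1.3 for uncommon events, falls towards 1 for very common ones, and there is almost no bias for events confined to the first weeks.

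The documents do not support the stronger reading that equal hazards will generally appear as excess afatinib toxicity. That depends on steady accrual of events and on treatment time tracking PFS, and neither is stated. Safety is descriptive, with no AE test or decision rule, and for steadily accruing events the distortion runs against the sponsor's drug. This is therefore a cheap improvement to how the arms are compared, and the primary analysis is unaffected.

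**What to change.** In SAP 7.8.1, for the all-AE, grade 3 or higher, serious and discontinuation tables:

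1. Keep the crude percentages.
2. Add, by arm, the number of patients with a first event per patient-month at risk, counted from first dose to first event or to last dose plus 28 days, whichever is earlier.
3. Add time-to-first-event estimates at fixed early times such as weeks 6 and 12, censored at the end of the AE window. These compare the arms over the same period and handle early-onset events.
4. State that between-arm safety conclusions rest on all three together.

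The cost is a few extra outputs from first-dose, last-dose and onset dates that the planned tables already need. The person-time rate assumes a roughly constant hazard and can understate early-onset toxicity in the longer-exposed arm, so it must not be read alone. Because AEs can themselves end treatment, time at risk is not fully independent of toxicity, which is another reason to keep the crude percentages beside it.
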